#### **5.5.6.4 Injection Site Reaction and Pain**

Injection site reaction and pain are assessed every 6 months in the visual analogue scale (VAS) score (range 0-100mm) before and after IM depot injection at the scheduled visit. Descriptive statistics for VAS score will be tabulated by visit for the safety sample. Assessment pre 1st IM depot injection is used as baseline. Proportions of subjects rated as absent, mild, moderate and severe level by the investigator for localized pain, redness, swelling, and induration will be tabulated by visit for safety sample. In an addition, descriptive statistics for injection site reaction and pain are provided by order of injection.

#### **5.5.7 Other Data Analysis**

##### **5.5.7.1 Concomitant Medication**

Proportions of subjects from the enrolled sample taking concomitant medications will be tabulated by drug classification using the WHO drug prior to taking trial medication, in the trial period and in the follow-up period, respectively.

Proportions of subjects taking concomitant medications such as benzodiazepine and anticholinergic will be provided. Concomitant medications for benzodiazepine and anticholinergic will be converted into lorazepam equivalent and benztropine equivalent, respectively, using the appropriate conversion factors. Daily dose of benzodiazepine (lorazepam or equivalent) and anticholinergic (benztropine or equivalent) concomitant medications will be summarized. Daily dose for each subject is calculated in total dosage of the specific concomitant medications divided by the duration of subject in the trial period.

##### **5.5.7.2 Duration of Exposure to Trial Medication**

Exposure to aripiprazole IM depot for the enrolled sample will be summarized in percentage of subjects receiving injections, average dose level per injection and average trial day of receiving each injection. In an addition, percentage of subjects will be presented by dosing level per injection.

### **5.5.7.3 Compliance of Trial Medication**

To maintain subjects on a schedule within acceptable time window is critical for subjects to achieving and maintaining stability of psychotic symptoms for the completion of this depot trial. A missed dose of IM depot is defined as a lapse of > 38 days between injections. The minimum interval of 26 days and maximum interval of 38 days between injections is to ensure that therapeutic plasma concentrations of aripiprazole are maintained. Compliance of trial medication (aripiprazole IM Depot) will be summarized for the enrolled sample, in proportion of subjects having 100% compliance, along with the following key features of compliance:

- the intervals between Aripiprazole IM depot injections <26 days;
- missing at least 1 injection;
- missing 2 consecutive injections at any time in the trial;
- missing 3 injections within a 52-week time period.

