3.6.1.2 Injection and Assessments Performed Every Month

Monthly assessments (study months are every 4 weeks which is defined as 28 [-2/+10] days) include a C-SSRS assessment and recording of AEs experienced since the last visit and concomitant medications, followed by the aripiprazole IM Depot injection. The monthly injections and assessments should be performed on Study Months 1 through 104.

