3.11 Subject Compliance

Visit compliance is critical to achieving and maintaining stability of psychotic symptoms and to maintaining subjects on a schedule that will lead to completion of the IM Depot treatment within an acceptable time window. The key features of compliance can be summarized as follows:

- 1) IM depot injections are to be administered within an interval of 28 days between injections. The minimum allowable interval between IM depot injections is 26 days and the maximum interval is 38 days. Every effort should be made to adhere to the 28-day cycle.
- 2) If a subject misses 2 consecutive injections at any time in the study, or if a subject misses 3 injections in a 52-week time period, then this subject is considered noncompliant and must be withdrawn from the study.

Evaluations conducted outside of the windows defined in [Table 3.6-1](#) will be considered deviations, but will not impact the subject’s ability to continue the study.

Protocol 31-10-270

Visit windows are provided not only to allow flexibility with scheduling, but also to assure an adequate supply of study medication between injections. If a subject misses an injection, the injection should be given at the earliest opportunity. A missed dose of IM depot is defined as a lapse of > 38 days between injections. The minimum interval of 26 days and maximum interval of 38 days between injections is to ensure that therapeutic plasma concentrations of aripiprazole are maintained.

The time and date of each dose of aripiprazole IM Depot will be recorded on the CRF. If a dose was not administered as scheduled, an explanation will be provided in the CRF and supported by source documentation. The accountability of IM depot vials will be maintained at the vial level. Subjects who, in the investigator's judgment, are noncompliant with the IM depot injection schedule should be counseled on the importance of adhering to the treatment schedule. Reasons for noncompliance should be determined, if possible. Investigators should use their judgment to assess the feasibility of continuing subjects in the study who are significantly noncompliant.

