## **5.2 Disposition of Subjects**

Disposition of subjects for the enrolled sample will be summarized by region, country and center. Subject duration by month and reason for discontinuation will be tabulated for the enrolled sample. Subjects who are evaluated at last scheduled visit during the treatment period are defined as completers. Subjects who are evaluated at the last scheduled visit during the treatment period are defined as completers, i.e., subjects who have their last scheduled visit, or who discontinue due to the commercial availability of trial drug in the country are defined as completers.

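### The missed-dose rule in SAP 5.5.7.3 needs a later injection to close the gap, so subjects withdrawn for missing doses can drop out of the rows meant to count them

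*SAP*

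**What the plan says.** SAP 5.5.7.3 defines a missed dose in one sentence: "A missed dose of IM depot is defined as a lapse of > 38 days between injections". It then summarises compliance in the enrolled sample, "in proportion of subjects having 100% compliance", with separate rows for intervals under 26 days, at least one missed injection, "missing 2 consecutive injections at any time in the trial" and "missing 3 injections within a 52-week time period". The SAP does not define 100% compliance, does not say how to treat the time after the last injection, and does not say how long one gap must be to count as two misses. SAP 5.1.3 adds that missing data are not imputed.

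Protocol 3.11 uses the same missed-dose definition and attaches a consequence to the two thresholds. Two consecutive misses lead to withdrawal, and "if a subject misses 3 injections in a 52-week time period, then this subject is considered noncompliant and must be withdrawn". Protocol 3.7.3, item 8, repeats the requirement. On data, Protocol 3.11 states: "The time and date of each dose of aripiprazole IM Depot will be recorded on the CRF". It also asks for a CRF explanation of any dose not given on schedule. SAP 5.2 plans the end-of-participation data: "Subject duration by month and reason for discontinuation will be tabulated for the enrolled sample".

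**The concern.** An interval between injections has an injection at each end. A subject who reaches a withdrawal threshold and is managed as the protocol requires gets no further study injection, so the gap that took the subject over the threshold is normally left open. Under the literal rule that gap contributes nothing. The rows for two consecutive and for three missed injections can then leave out the subjects they are meant to describe. A subject with no earlier lapse also disappears from the row for at least one miss.

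A second weakness concerns gaps that are closed. The rule counts lapses, not doses, so a single gap long enough to skip two scheduled doses still scores one.

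What is at stake is the accuracy of one table. A reader would use it to judge how well monthly dosing was maintained, and it could look better than it was.

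**Working it through.** **The plan's own limits.** The dosing window is 28 (−2/+10) days (Protocol 3.1). 28 − 2 = 26 and 28 + 10 = 38, which reproduces the stated minimum and maximum intervals.

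**How many misses in one gap.** The documents give no day count for a second miss, so two assumptions are compared.

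- Schedule fixed from the last injection: dose *k* has the window 28*k* − 2 to 28*k* + 10, so the second dose is missed after day 2 × 28 + 10 = 66. For a gap G above 38 days, misses = ceil((G − 38)/28).
- Maximum interval stacked: the second dose is missed after day 2 × 38 = 76.

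**Constructed histories.** *Literal* uses only intervals closed by a later injection. *Full* adds the open interval to withdrawal and counts doses within a gap.

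| Case | Closed intervals (days) | Open interval at withdrawal | Literal | Full | Row missed under the literal rule |
|---|---|---|---|---|---|
| A | 28 × 6 | 77 | 0 | 2 | two consecutive; at least one |
| B | 28, 28, 42, 28, 28, 42, 28 | 45 | 2 | 3 | three in 52 weeks |
| C | 45 | 39 | 1 | 2, adjacent | two consecutive |
| D | 78 | none | 1 | 2 | two consecutive |

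- A: last injection on day 168, withdrawal on day 168 + 77 = 245. (77 − 38)/28 = 1.39, rounded up to 2; 77 also exceeds 76.
- B: the closed intervals sum to 224 days and withdrawal is on day 224 + 45 = 269, inside 52 × 7 = 364 days. Misses are 1 + 1 from the two 42-day intervals, plus 1 from the open 45 days.
- C: 1 from the closed 45 days plus 1 from the open 39 days.
- D: (78 − 38)/28 = 1.43, rounded up to 2; 78 also exceeds 76.

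All four results are the same under both assumptions. They differ for gaps of 67 to 76 days (2 misses against 1). An open gap of that length scores 0 under the literal rule either way.

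**Choice of closing date.** Three convenient end dates would create false misses:

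- Treatment that ends for commercial availability may stop about 6 weeks after the last injection (Protocol 3.1): 42 > 38.
- The follow-up call comes 30 ± 3 days after the decision that the subject will leave. A decision on day 28 could put the call on day 28 + 33 = 61 > 38.
- A subject who stops for an adverse event on day 20 and attends a termination visit on day 45 would score a miss, because 45 > 38, although no dose was overdue when treatment stopped.

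**The case against.** The best defence is that the literal reading is not the intended one. The definition comes from Protocol 3.11, where it sits beside a rule to withdraw subjects who miss injections. If a gap had to be closed by a later dose before it counted, a subject who simply stopped attending could never trigger that rule. An ongoing gap must therefore count in the protocol, and a sensible programmer would read the SAP the same way. The CRF also records why a scheduled dose was not given. SAP 5.5.7.4 points to a separate deviation specification that may contain derivations, and reasons for discontinuation are tabulated, so the withdrawals stay visible.

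Much of this stands. It shows what the count should be, and that omission is not inevitable. But SAP 5.5.7.3 ties its rows neither to the CRF explanations nor to the deviation specification, which is not among the documents. The one rule it states gives the wrong count in the cases above, and a discontinuation table does not correct the compliance rows.

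A reader might infer more than the documents support:

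- *Two adjacent 39-day intervals with both injections given are wrongly counted as two consecutive misses.* They are not. Under Protocol 3.11 any lapse beyond 38 days is a missed dose even when the injection is given later, so counting both follows the definition. Case C relies on the same principle.
- *The third miss is never counted.* It is counted whenever the late third injection is given, because that closes the gap.
- *Withdrawn subjects will be reported as 100% compliant.* This could happen in Case A, but the SAP does not define that category.

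**Conclusion.** The point holds and is minor. Applied as written, SAP 5.5.7.3 can leave a subject withdrawn for missed doses out of the row for that criterion and, with no earlier lapse, out of the row for at least one miss. It also scores a closed gap that spans two doses as one. In the constructed cases each count is short by one or two misses. The closed-gap case should be the less usual one, since a subject who has missed two doses should already have been withdrawn.

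The number of subjects affected cannot be estimated: the documents expect 500 to 800 enrolled but give no rate of missed doses. Only the descriptive compliance summary is touched. No analysis sample and no other safety summary uses these counts, so nothing here supports an inference that the safety results are biased.

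The conclusion about open gaps rests only on the wording of the rule and the withdrawal requirement. The number of misses within a single long gap rests on an assumed day threshold; Cases A and D do not depend on which of the two is chosen.

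**What to change.** Amend SAP 5.5.7.3 only.

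1. Define a miss as no injection within 38 days of the previous one.
2. Count the open interval from the last injection to the date of the decision to stop treatment or withdraw the subject, or to last contact if the subject is lost to follow-up. Do not close it at the last injection itself, at a later termination visit or at the follow-up call.
3. Exclude completers and administrative ends of treatment from step 2.
4. State the day threshold at which one gap counts as two misses, for example more than 66 days, and declare it as an assumption.
5. State that misses in adjacent gaps count as consecutive, in line with the protocol's definition.
6. Check the counts against the CRF explanations for doses not given.

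The cost is a little programming. Injection dates are on the CRF, and the planned disposition tables already need an end of participation and a reason for each subject, so no new data and no protocol amendment are needed. The compliance figures may look slightly less favourable. One limit remains: closing at last contact counts no misses after a lost subject was last reached.

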### **5.5.7.4 Protocol Deviation**

Protocol deviations will be listed, and tabulated by protocol deviation type, country and centers. Protocol deviations are specified in the separate documentation: *Programmable Deviation Specification for Protocol 31-10-270*.

**Appendix 1 Clinical Relevance Criteria for Laboratory Test Abnormalities**

Laboratory Tests	Criterion Values
Chemistrya	
AST(SGOT)	≥ 3x upper limit of normal (ULN)
ALT(SGPT)	≥ 3x ULN
Alkaline Phosphates	≥ 3x ULN
LDH	≥ 3x ULN
BUN	≥ 30 mg/dl
Creatinine	≥ 2.0 mg/dl
Uric Acid	
Male	≥ 10.5 mg/dl
Female	≥ 8.5 mg/dl
Bilirubin (Total)	≥ 2.0mg/dl
CPK	≥ 3xULN
Prolactin	>ULN
Hematologya	
Hematocrit	
Male	≤ 37% and ≥ 3% decrease from baseline
Female	≤ 32% and ≥ 3% decrease from baseline
Hemoglobin	
Male	≤ 11.5 g/dl
Female	≤ 9.5 g/dl
White Blood Count	≤ 2,800 /mm  or ≥ 16,000 /mm 
Eosinophils	≥ 10%
Neutrophils	≤ 15%
Platelet Count	≤ 75,000 /mm  or ≥ 700,000 /mm 
Urinalysisa	
Protein	Increase of ≥ 2 units
Glucose	Increase of ≥ 2 units
Casts	Increase of ≥ 2 units
Additional Criteria	
Chloride	≤90 mEq/L or ≥ 118 mEq/L
Potassium	≤2.5 mEq/L or ≥ 6.5 mEq/L
Sodium	≤126 mEq/L or ≥ 156 mEq/L
Calcium	≤8.2 mg/dL or ≥ 12 mg/dL
Glucose	
Fasting	≥ 115 mg/dL
Non-Fasting	≥ 200 mg/dL
Total cholesterol, Fasting	≥ 240 mg/dL
LDL cholesterol, Fasting	≥ 160mg/dL
HDL cholesterol, Fasting	≤ 30 mg/dL
Triglycerides, Fasting	
Male	≥ 160 mg/dL
Female	≥ 120 mg/dL

a As defined in “Supplementary Suggestions for Preparing an Integrated Summary of Safety Information in an Original NDA Submission and for Organizing Information in Periodic Safety Updates,” FDA Division of Neuropharmacological Drug Products draft (2/27/87).

**Appendix 2 Clinical Relevance Criteria for Vital Sign Abnormalities**

VARIABLE	CRITERION VALUE a	CHANGE RELATIVE TO BASELINE a
HEART RATE b	>120 BPM <50 BPM	INCREASE OF ≥ 15 DECREASE OF ≥ 15
SYSTOLIC BLOOD PRESSURE b	>180 MMHG <90 MMHG	INCREASE OF ≥ 20 DECREASE OF ≥ 20
DIASTOLIC BLOOD PRESSURE b	>105 MMHG <50 MMHG	INCREASE OF ≥ 15 DECREASE OF ≥ 15
ORTHOSTATIC HYPOTENSION	≥ 20 MMHG DECREASE IN SYSTOLIC BLOOD PRESSURE AND ≥ 25 BPM INCREASE IN HEART RATE FROM SUPINE TO SITTING/STANDING	
WEIGHT	-	INCREASE ≥ 7% DECEASE ≥ 7%
TEMPRATURE	≥37.8°C	INCREASE ≥1.1°C

a In order to be identified as “clinically relevantly abnormal,” an on-drug value must meet the “Criterion Value” and also represent a change from the patient’s pretreatment value of at least the magnitude shown in the “Change Relative to Baseline column.

b As defined in “supplementary suggestions for Preparing an integrated Summary of Safety Information in an Original NDA Submission and for Organizing Information in period safety Updates,” FDA Division of Neuropharmacological Drug Products draft (2/27/87)

**Appendix 3 Clinical Relevance Criteria for ECG Abnormalities**

Variable	Criteria/Change relative to Baseline
Rate	
Tachycardia	≥ 120 bpm and increase of ≥ 15 bpm
Bradycardia	≤ 50 bpm and decrease of ≥ 15 bpm
Rhythm	
Sinus tachycardia	≥ 120 bpm and increase of ≥ 15 bpm
Sinus bradycardia	≤ 50 bpm and decrease of ≥ 15 bpm
Supraventricular premature beat	Not present → present
Ventricular premature beat	Not present → present
Supraventricular tachycardia	Not present → present
Ventricular tachycardia	Not present → present
Atrial fibrillation	Not present → present
Atrial flutter	Not present → present
Conduction	
1  A-V Block	PR ≥ 0.20 sec and increase of ≥ 0.05 sec
2  A-V Block	Not present → present
3  A-V Block	Not present → present
Left bundle-branch block	Not present → present
Right bundle-branch block	Not present → present
Pre-excitation syndrome	Not present → present
Other intraventricular conduction block	QRS ≥ 0.12 sec and increase of ≥ 0.02 sec
Infarction	
Acute or Subacute	Not present → present
Old	Not present - present at ≥ 12 weeks post entry into the trial
ST/T Morphology	
Myocardial Ischemia	Not present → present
Symmetrical T-wave inversion	Not present → present
QTc	≥ 450 msec and ≥ 10% increase from baseline

## Appendix 4 Table of Contents for Tables and Listings

### Clinical Summary Tables

CT-1.1	SUBJECT DISPOSITION
CT-1.2	SUBJECT DISPOSITION BY REGION, COUNTRY AND CENTER
CT-1.3	SUBJECT DURATION BY MONTH
CT-1.4	ENROLLMENT BY COUNTRY
CT-1.5	ENROLLMENT BY COUNTRY BY AGE GROUP
CT-2	REASONS FOR DISCONTINUATION
CT-3	DEMOGRAPHIC CHARACTERISTICS BY SEX
CT-4.1	CONCOMITANT MEDICATIONS TAKEN PRIOR TO STUDY PERIOD
CT-4.2	CONCOMITANT MEDICATIONS TAKEN DURING STUDY PERIOD
CT-4.3	CONCOMITANT MEDICATIONS TAKEN POST STUDY PERIOD
CT-4.4	CONCOMITANT BENZODIAZEPINES AND ANTICHOLINERGICS USE
CT-5	CGI SEVERITY SCORE - MEAN CHANGE FROM BASELINE BY MONTH - OC
CT-6.1.1	SIMPSON-ANGUS SCALE TOTAL SCORE - MEAN CHANGE FROM BASELINE BY MONTH - OC
CT-6.1.2	BARNES AKATHISIA GLOBAL SCORE - MEAN CHANGE FROM BASELINE BY MONTH - OC
CT-6.1.3	AIMS MOVEMENT RATING SCORE - MEAN CHANGE FROM BASELINE BY MONTH - OC
CT-6.2.1	COLUMBIA-SUICIDE SEVERITY RATING SCALE (C-SSRS) - INCIDENCE OF SUICIDALITY
CT-6.2.2	COLUMBIA-SUICIDE SEVERITY RATING SCALE (C-SSRS) - INCIDENCE OF SUICIDALITY BY TYPE
CT-6.2.3	COLUMBIA-SUICIDE SEVERITY RATING SCALE (C-SSRS) - MEAN CHANGE FROM BASELINE IN SUICIDAL IDEATION INTENSITY TOTAL SCORE
CT-7.1	EXTENT OF EXPOSURE TO STUDY MEDICATION - ARIPIPRAZOLE IM DEPOT
CT-7.2	DESCRIPTIVE STATISTICS FOR STUDY DAYS OF ARIPIPRAZOLE IM DEPOT INJECTIONS
CT-7.3	EXTENT OF EXPOSURE TO STUDY MEDICATION BY INJECTION DOSE - ARIPIPRAZOLE IM DEPOT
CT-8.1	INCIDENCE OF ADVERSE EVENTS (ALL CAUSALITIES)
CT-8.2.1	INCIDENCE OF TREATMENT-EMERGENT ADVERSE EVENTS BY SYSTEM ORGAN CLASS
CT-8.2.2	INCIDENCE OF TREATMENT-EMERGENT ADVERSE EVENTS BY SYSTEM ORGAN CLASS AND MEDDRA PREFERRED TERM
CT-8.2.3	INCIDENCE OF TREATMENT-EMERGENT ADVERSE EVENTS BY SYSTEM ORGAN CLASS, MEDDRA PREFERRED TERM AND SEVERITY
CT-8.2.4.1	INCIDENCE OF TREATMENT-EMERGENT ADVERSE EVENTS GREATER THAN 5% BY SYSTEM ORGAN CLASS AND MEDDRA PREFERRED TERM
CT-8.2.4.2	INCIDENCE OF TREATMENT-EMERGENT ADVERSE EVENTS BY MEDDRA PREFERRED TERM IN DESCENDING ORDER OF INCIDENCE RATE FOR TOTAL
CT-8.2.4.3	INCIDENCE OF NON-SERIOUS TREATMENT-EMERGENT ADVERSE EVENTS OCCURRING IN AT LEAST 5% OF THE SUBJECTS BY SYSTEM ORGAN CLASS AND MEDDRA PREFERRED TERM
CT-8.2.4.4	OCCURRENCE (NUMBER OF EVENTS) OF NON-SERIOUS TREATMENT-EMERGENT ADVERSE EVENTS BY SYSTEM ORGAN CLASS AND MEDDRA PREFERRED TERM
CT-8.2.5	INCIDENCE OF TREATMENT-EMERGENT EPS ADVERSE EVENTS
CT-8.2.6	INCIDENCE OF TREATMENT-EMERGENT ADVERSE EVENTS RELATED TO SUICIDAL IDEATION/SUICIDE BY SYSTEM ORGAN CLASS AND MEDDRA PREFERRED TERM
CT-8.2.7	INCIDENCE OF TREATMENT-EMERGENT ADVERSE EVENTS RELATED TO INJECTION SITE BY SYSTEM ORGAN CLASS AND MEDDRA PREFERRED TERM
CT-8.2.8	INCIDENCE OF TREATMENT-EMERGENT ADVERSE EVENTS RELATED TO GLUCOSE METABOLISM BY SYSTEM ORGAN CLASS AND MEDDRA PREFERRED TERM
CT-8.2.9	INCIDENCE OF TREATMENT-EMERGENT ADVERSE EVENTS RELATED TO QT INTERVAL ABNORMALITIES BY SYSTEM ORGAN CLASS AND MEDDRA PREFERRED TERM
CT-8.2.10	INCIDENCE OF TREATMENT-EMERGENT ADVERSE EVENTS RELATED TO EFFECTS ON PROLACTIN BY SYSTEM ORGAN CLASS AND MEDDRA PREFERRED TERM
CT-8.2.11	INCIDENCE OF TREATMENT-EMERGENT ADVERSE EVENTS RELATED TO WBC ABNORMALITIES BY SYSTEM ORGAN CLASS AND MEDDRA PREFERRED TERM
CT-8.2.12	INCIDENCE OF TREATMENT-EMERGENT ADVERSE EVENTS RELATED TO ORTHOSTASIS BY SYSTEM ORGAN CLASS AND MEDDRA PREFERRED TERM
CT-8.2.13	INCIDENCE OF TREATMENT-EMERGENT ADVERSE EVENTS RELATED TO LIPID PARAMETERS BY SYSTEM ORGAN CLASS AND MEDDRA PREFERRED TERM
CT-8.2.14	INCIDENCE OF TREATMENT-EMERGENT ADVERSE EVENTS RELATED TO WEIGHT BY SYSTEM ORGAN CLASS AND MEDDRA PREFERRED TERM
CT-8.3.1	INCIDENCE OF POTENTIALLY DRUG-RELATED TREATMENT-EMERGENT ADVERSE EVENTS BY SYSTEM ORGAN CLASS
CT-8.3.2	INCIDENCE OF POTENTIALLY DRUG-RELATED TREATMENT-EMERGENT ADVERSE EVENTS BY SYSTEM ORGAN CLASS AND MEDDRA PREFERRED TERM
CT-8.3.3	INCIDENCE OF POTENTIALLY DRUG-RELATED TREATMENT-EMERGENT ADVERSE EVENTS BY SYSTEM ORGAN CLASS, MEDDRA PREFERRED TERM AND SEVERITY
CT-8.4.1	INCIDENCE OF DEATHS DUE TO TREATMENT-EMERGENT ADVERSE EVENTS BY SYSTEM ORGAN CLASS AND MEDDRA PREFERRED TERM
CT-8.5.1	INCIDENCE OF SERIOUS TREATMENT-EMERGENT ADVERSE EVENTS BY SYSTEM ORGAN CLASS

## Protocol 31-10-270 Statistical Analysis Plan

CT-8.5.2	INCIDENCE OF SERIOUS TREATMENT-EMERGENT ADVERSE EVENTS BY SYSTEM ORGAN CLASS AND MEDDRA PREFERRED TERM
CT-8.5.3	INCIDENCE OF SERIOUS TREATMENT-EMERGENT ADVERSE EVENTS BY SYSTEM ORGAN CLASS AND MEDDRA PREFERRED TERM AND SEVERITY
CT-8.5.4	OCCURRENCES (NUMBER OF EVENTS) OF SERIOUS TREATMENT-EMERGENT ADVERSE EVENTS BY SYSTEM ORGAN CLASS AND MEDDRA PREFERRED TERM
CT-8.5.5	OCCURRENCES (NUMBER OF EVENTS) OF POTENTIALLY DRUG-RELATED SERIOUS TREATMENT-EMERGENT ADVERSE EVENTS BY SYSTEM ORGAN CLASS AND MEDDRA PREFERRED TERM
CT-8.6.1	INCIDENCE OF TREATMENT-EMERGENT ADVERSE EVENTS RESULTING IN DISCONTINUATIONS OF STUDY MEDICATION BY SYSTEM ORGAN CLASS
CT-8.6.2	INCIDENCE OF TREATMENT-EMERGENT ADVERSE EVENTS RESULTING IN DISCONTINUATIONS OF STUDY MEDICATION BY SYSTEM ORGAN CLASS AND MEDDRA PREFERRED TERM
CT-8.6.3	INCIDENCE OF TREATMENT-EMERGENT ADVERSE EVENTS RESULTING IN DISCONTINUATIONS OF STUDY MEDICATION BY SYSTEM ORGAN CLASS, MEDDRA PREFERRED TERM AND SEVERITY
CT-9.1	LISTING OF DEATHS
CT-9.2	LISTING OF SERIOUS ADVERSE EVENTS
CT-9.3	LISTING OF DISCONTINUATIONS DUE TO ADVERSE EVENTS
CT-9.4	LISTING OF ADVERSE EVENTS RELATED TO SUICIDAL IDEATION/SUICIDE
CT-9.5	LISTING OF POTENTIAL HY'S LAW CASES
CT-10.1	LISTING OF LABORATORY VALUES OF POTENTIAL CLINICAL RELEVANCE BY SUBJECT
CT-10.2	LISTING OF LABORATORY VALUES OF POTENTIAL CLINICAL RELEVANCE BY TEST
CT-10.3	CRITERIA FOR LABORATORY VALUES OF POTENTIAL CLINICAL RELEVANCE
CT-10.4	CRITERIA FOR LABORATORY VALUES OF POTENTIAL CLINICAL RELEVANCE REVISED
CT-11.1	LISTING OF VITAL SIGNS OF POTENTIAL CLINICAL RELEVANCE BY SUBJECT
CT-11.2	CRITERIA FOR POTENTIALLY CLINICALLY RELEVANT VITAL SIGN ABNORMALITIES
CT-12.1	LISTING OF ECG MEASUREMENTS OF POTENTIAL CLINICAL RELEVANCE
CT-12.2	CRITERIA FOR ECG MEASUREMENTS OF POTENTIAL CLINICAL RELEVANCE
CT-12.3	ECG DIAGNOSIS MAPPING FOR ECG MEASUREMENTS OF POTENTIAL CLINICAL RELEVANCE
CT-13.1.1	INCIDENCE OF LABORATORY VALUES OF POTENTIAL CLINICAL RELEVANCE
CT-13.1.2	INCIDENCE OF POTENTIALLY CLINICALLY RELEVANT SHIFTS IN LIPIDS
CT-13.1.3	INCIDENCE OF POTENTIALLY CLINICALLY RELEVANT SHIFTS IN GLUCOSE
CT-13.1.4	INCIDENCE OF LABORATORY VALUES OF POTENTIAL CLINICAL RELEVANCE REVISED
CT-13.2.1	LABORATORY TEST RESULTS FOR SERUM CHEMISTRY - MEAN CHANGE FROM BASELINE
CT-13.2.2	LABORATORY TEST RESULTS FOR HEMATOLOGY - MEAN CHANGE FROM BASELINE
CT-13.2.3	LABORATORY TEST RESULTS FOR URINALYSIS - MEAN CHANGE FROM BASELINE
CT-13.2.4	LABORATORY TEST RESULTS FOR OTHER LABORATORY TESTS - MEAN CHANGE FROM BASELINE
CT-13.2.5.1	INCIDENCE OF PROLACTIN LEVEL ABOVE UPPER LIMIT OF NORMAL RANGE BY SEX
CT-13.2.5.2	LABORATORY TEST RESULTS FOR PROLACTIN - MEAN CHANGE FROM BASELINE BY SEX
CT-14.1	INCIDENCE OF VITAL SIGNS OF POTENTIAL CLINICAL RELEVANCE
CT-14.2	INCIDENCE OF POTENTIALLY CLINICALLY RELEVANT WEIGHT GAIN OR LOSS
CT-14.3	MEAN CHANGE FROM BASELINE IN VITAL SIGNS PARAMETERS
CT-15.1	INCIDENCE OF ECG MEASUREMENTS OF POTENTIAL CLINICAL RELEVANCE
CT-15.2	ECG PARAMETERS - MEAN CHANGE FROM BASELINE
CT-15.3	INCIDENCE OF CATEGORICAL INCREASES IN ECG - QTC
CT-16.1	VISUAL ANALOG SCALE SCORE FOR SUBJECT-REPORTED RATING OF PAIN AT MOST RECENT INJECTION SITE - MEAN SCORE
CT-16.2.1	PROPORTION OF SUBJECTS AT EACH LEVEL OF INVESTIGATOR'S ASSESSMENT OF MOST RECENT INJECTION SITE - PAIN
CT-16.2.2	PROPORTION OF SUBJECTS AT EACH LEVEL OF INVESTIGATOR'S ASSESSMENT OF MOST RECENT INJECTION SITE - SWELLING
CT-16.2.3	PROPORTION OF SUBJECTS AT EACH LEVEL OF INVESTIGATOR'S ASSESSMENT OF MOST RECENT INJECTION SITE - REDNESS
CT-16.2.4	PROPORTION OF SUBJECTS AT EACH LEVEL OF INVESTIGATOR'S ASSESSMENT OF MOST RECENT INJECTION SITE - INDURATION
CT-17.1	INCIDENCE OF TREATMENT-EMERGENT ADVERSE EVENTS BY SYSTEM ORGAN CLASS AND MEDDRA PREFERRED TERM BY REGION (US VS NON-US)
CT-17.2	INCIDENCE OF TREATMENT-EMERGENT ADVERSE EVENTS BY SYSTEM ORGAN CLASS AND MEDDRA PREFERRED TERM BY SEX
CT-17.3	INCIDENCE OF TREATMENT-EMERGENT ADVERSE EVENTS BY SYSTEM ORGAN CLASS AND MEDDRA PREFERRED TERM BY RACE
CT-17.4	INCIDENCE OF TREATMENT-EMERGENT ADVERSE EVENTS BY SYSTEM ORGAN CLASS AND MEDDRA PREFERRED TERM BY AGE GROUP
CT-17.5	INCIDENCE OF TREATMENT-EMERGENT ADVERSE EVENTS BY SYSTEM ORGAN CLASS AND MEDDRA PREFERRED TERM BY ETHNICITY
CT-17.6	INCIDENCE OF TREATMENT-EMERGENT ADVERSE EVENTS BY SYSTEM ORGAN CLASS AND MEDDRA PREFERRED TERM BY BMI
CT-18.1	VISUAL ANALOG SCALE SCORE FOR SUBJECT-REPORTED RATING OF PAIN AT MOST RECENT INJECTION SITE - MEAN SCORE BY INJECTION

